## **G Statistical Analysis Plan**

### **G1 Sample Size Determination and Power**

The goal of the pilot is to test the feasibility of the Adapted LiFE for medically underserved population, and is not hypothesis testing. Thus, sample size calculation are not necessary. We select to set our sample size at 16 to evaluate feasibility and effect size for future study.

---

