### A1 Study Abstract

The purpose of this study is to pilot test the feasibility of a study design for future larger trial of Adapted LiFE among medically underserved older adults. We will evaluate if : 1) Adapted LiFE is feasible for medically underserved older adults, and 2) the study design is feasible with working randomization module and appropriate measurements.

Feasibility outcome measures include reach, acceptance, adherence, fidelity, safety, and appropriate efficacy outcome selection for balance, lower extremity muscle strength, and habit formation.

We will conduct a pilot RCT with an attentional control group. The treatment (Adapted LiFE) group (n=8) will receive 7-sessions of culturally Adapted LiFE over 12 weeks, while the attentional control group (n=8) will receive the same amount from an interventionist with a gentle flexibility program "Go4life" developed by the National Institute on Aging during intervention period.

We will recruit older adults who: are age 70 or older; self-report falls in the past 12 months; and reside in a medically underserved area. We will exclude participants who: have attention and memory impairment (Short Blessed Test score  $\geq 8$ ), are unable to stand with assistive devices, are severely depressed (The Geriatric Depression Scale  $\geq 10$ ), and have serious health conditions for which exercise is contraindicated. Paired t-tests will be used to test time effects, and independent t-tests will be used to test group effects of Adapted LiFE.

---

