## **2.d Randomization Method and Blinding**

After the consent process, the pre-test could be administered immediately or be scheduled at a different day. After pre-test, participants will be randomized immediately by a pre-programed REDCap (Research Electronic Data Capture) module. REDCap (Research Electronic Data Capture) is a secure, web-based application designed exclusively to support data capture for research studies. A blinded rater will conduct the post-test and phone follow-up.

Participants will not be blinded to which group they are in. The REDCap module uses a blocked randomization design in which gender will be stratified to ensure balanced group sizes. A block size of 2 and an allocation ratio of 1:1 based on gender. Then, based on group allocation, the occupational therapy (OT) interventionist will start either Adapted LiFE or the attention control intervention.

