## **G3 Statistical Methods**

To detect effect of intervention. Wilcoxon signed rank tests will be used to identify trends in levels of balance, muscle strength, and habit formation.

To detect effect of intervention. Wilcoxon signed rank tests will be used to identify trends in levels of balance, muscle strength, and habit formation.

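### G1 gives evaluating effect size as a reason for N=16, but 8 per arm estimates an unadjusted between-arm difference only to within about 1 SD, and G3 names no between-arm analysis

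*Combined protocol and SAP*

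**What the plan says.** G1 gives the total of 16 and two reasons for it: "We select to set our sample size at 16 to evaluate feasibility and effect size for future study". The same paragraph says "The goal of the pilot is to test the feasibility of the Adapted LiFE for medically underserved population, and is not hypothesis testing" and concludes "Thus, sample size calculation are not necessary". It gives no precision target.

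The abstract (A1) splits the 16 into two arms of 8. For the treatment arm it says "The treatment (Adapted LiFE) group (n=8) will receive 7-sessions of culturally Adapted LiFE over 12 weeks"; the control arm has the same number. Section 2.d confirms equal allocation: "A block size of 2 and an allocation ratio of 1:1 based on gender".

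Three sections describe the efficacy analysis or purpose, and they do not agree:
- **G3** opens "To detect effect of intervention" and names Wilcoxon signed rank tests for balance, muscle strength and habit formation. It names no between-arm comparison and no confidence interval.
- **A1** plans paired t-tests for change over time and independent t-tests for the group effect.
- **E1** lists the pilot's purposes as trying out the protocol, estimating recruitment and retention, and validating the tools. Effect size is not among them.

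**The concern.** G1 appears under the sample size heading and links the pilot's effect size to a future study, so a reader planning that study may take the observed effect as a design value. Nothing in the plan warns how imprecise it will be, and no interval is promised that would show it.

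The stated analysis does not serve the stated purpose either. A signed rank test on pre- and post-test values describes change within participants. In a trial with an attention control, the effect needed for planning is the difference between arms. A1 has a test for that difference and G3 does not, while G1 says no hypotheses are tested. The analyst therefore cannot tell which analysis is intended or what may be concluded from it.

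At stake is how the pilot is used: a chance large or small estimate could be carried forward as if it were informative.

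**Working it through.** **Inputs from the documents.** 16 participants (G1), 8 per arm (A1), ratio 1:1 (2.d); 8 + 8 = 16 agrees. G1 gives no alpha, power, SD or target difference, so there is no calculation to reproduce.

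**Assumptions, not in the documents.** Two-sided 95% level; normal outcomes with equal SD; true standardised difference d of 0.3, 0.4, 0.5 or 0.8; main trial at two-sided 5% and 80% power.

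**Step 1: precision at 8 per arm.** In SD units, the SE of the unadjusted difference is √(1/8 + 1/8) = 0.50.
- Normal quantile: 1.96 × 0.50 = 0.98 SD.
- t on 14 df: 2.145 × 0.50 = 1.07 SD.

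The exact noncentral-t 95% interval is −0.69 to 1.28 for an observed d of 0.3, −0.51 to 1.49 for 0.5, and −0.24 to 1.81 for 0.8. All three include zero.

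**Step 2: at the plan's own retention target.** C1 aims for 80% retention: 0.80 × 16 = 12.8, about 13. Section 1.i of the study procedures deletes withdrawn participants' outcome data. With 7 + 6 analysed, SE = √(1/7 + 1/6) = 0.556, and the half-width is 1.96 × 0.556 = 1.09 SD or, by t on 11 df, 2.201 × 0.556 = 1.22 SD.

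**Step 3: if the observed effect sized the main trial.**
- Wrong sign: Φ(−d/0.50).
- Power of the pilot's independent t-test: noncentral t, 14 df, noncentrality d/0.50.
- Main-trial n per arm: 2 × (1.960 + 0.842)² / d², rounded up.
- Implied n varies as 1/(observed d)². It is under half the need when observed d exceeds d√2. It is over double, or undefined, when observed d is below d/√2. Both probabilities are from the noncentral t.

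| True d (assumed) | n per arm needed | Wrong sign | Power of pilot test | Implied n under half | Implied n over double, or none |
|---|---|---|---|---|---|
| 0.3 | 175 | 27% | 9% | 41% | 43% |
| 0.4 | 99 | 21% | 12% | 38% | 40% |
| 0.5 | 63 | 16% | 15% | 35% | 38% |
| 0.8 | 25 | 5% | 32% | 28% | 32% |

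The last column includes the wrong-sign pilots.

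**Step 4: effect of baseline adjustment.** With correlation r between T1 and T2, the half-width is about 2.160 × 0.50 × √(1 − r²) (t, 13 df): 0.94 SD at r = 0.5, 0.77 at r = 0.7, 0.47 at r = 0.9. The documents give no r and plan no adjustment.

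**Step 5: precision of the SD.** On 14 df, the 95% limits for the pooled SD are √(14/26.12) = 0.73 and √(14/5.63) = 1.58 times the estimate.

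**The case against.** A pilot does not need a power calculation, and N=16 without one can be acceptable for feasibility. That stands: the point concerns only the second reason given for N.

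A reader might infer three stronger things that the documents do not support:
- **That the main trial will be mis-sized.** No section says the pilot's effect will enter a sample size formula. G1 implies it by its wording and heading; E1 and the primary aim in C1 point to feasibility. The harm is conditional.
- **That a non-significant result would stop the programme or be read as no effect.** Every numerical target in C1 is a feasibility threshold, and no efficacy p-value is a criterion for proceeding. B2 ties the decision to the pilot's results in general.
- **That the main trial would usually be too small.** Step 3 shows errors of similar frequency in both directions, and their size depends on a true effect that the documents do not give.

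It is also fair to say that the figure of about 1 SD belongs to an unadjusted difference. The plan does not define its effect size, and T1 values are collected, so a strongly correlated baseline could narrow the interval. Since no adjustment is planned, the unadjusted figure is the reasonable default, labelled as such.

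**Conclusion.** The concern holds as a limited point. Sixteen participants cannot evaluate a between-arm effect size with useful precision: the unadjusted 95% half-width is 0.98 to 1.07 SD with complete data and 1.09 to 1.22 SD at the plan's retention target. G1, G3 and A1 also disagree on whether an effect is tested and by what method, and the test named in G3 does not estimate a between-arm effect.

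The precision figures need only 8 per arm and an unadjusted analysis. The wrong-sign rates (27% down to 5%) and pilot power (9% up to 32%) rest on assumed true effects of 0.3 to 0.8 SD. The consequence for the main trial depends further on a use of the estimate that the plan implies but does not state.

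**What to change.** - **G1:** remove effect size as a reason for 16. Say that the number serves the feasibility parameters, with outcome variability as a descriptive by-product.
- **G3:** replace the opening aim of detecting an effect with descriptive reporting of the between-arm difference in change, or a baseline-adjusted difference, with 95% confidence intervals and no significance claims.
- **A1:** bring the abstract's t-tests into line with G3.
- **Use of results:** state that the observed effect will not by itself be used to size the main trial. If the pilot SD is used, carry its uncertainty forward, for example by an upper confidence limit. How the later trial is sized can be left to its own protocol.

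The cost is a few sentences and a more modest stated purpose. No extra participants or procedures are needed.

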## **G2 Analysis Plan**

Data will be entered into REDCap. Descriptive statistics will be used to identify any trends in demographics, and feasibility outcomes.

## **G3 Statistical Methods**

To detect effect of intervention. Wilcoxon signed rank tests will be used to identify trends in levels of balance, muscle strength, and habit formation.

To detect effect of intervention. Wilcoxon signed rank tests will be used to identify trends in levels of balance, muscle strength, and habit formation.

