## **C Study Objectives**

### ***C1 Primary Aim***

The primary aim of this study is to establish feasibility of Adapted LiFE and a RCT design.

WE hypothesis that the feasibility pilot study will have high reach (60% recruitment and 80% retention rate of targeted participants), acceptance (80% of participants rating high satisfaction with Adapted LiFE), adherence (80% of all exercise activities achieved during the intervention period for each participant), fidelity (90% consistency of elements delivered by occupational therapists throughout the study period), safety (no adverse events caused by Adapted LiFE), and appropriate efficacy measurement selection (70% of the participants do not show floor/ceiling effects among balance, muscle strength, and habit outcomes at pre- and/or post-tests).

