### **E1 Overview of Study Design**

The pilot study will use RCT with an attentional control design (Figure 2). The purpose of the pilot study with the same design as the future main study is to test the study protocol, estimate recruitment/retention rate, and validate tools. This study design is appropriate for a future larger study because Adapted LiFE has strong face validity, good feasibility, and minimal risk when compared with structured exercise programs for medically underserved older adults.

We will recruit 16 participants and randomize them to receive 7 sessions of home visit and 1 booster phone call one month after the last session of Adapted LiFE or attention control (AC) intervention. Once an eligible participant is screened and consented in his/her home (T0 visit), the OT interventionist will either conduct or schedule the pre-test (T1). All pre- and post-tests will be conducted in participants' homes. After T1, the OT interventionist will randomize the participants to Adapted LiFE or the attention control group. The intervention period will start immediately after randomization and consist of seven sessions over 12 weeks. Post-tests (T2) will be conducted by a blinded OT rater after the last intervention session at the participant's home. Phone follow-ups (T3) will be conducted one month after post-test by a blinded OT rater. Any additional questions from the participants will also be addressed in the phone follow-up.

Feasibility outcomes such as reach, adherence, fidelity, and safety will be evaluated throughout the study session. Efficacy outcome such as balance and muscle strength will be evaluated at pre- test (T1), and post-test (T2). Habit formation will also be evaluated at T1, T2, and 1-month after post-test via phone.

*Figure 2. Overview of the feasibility pilot study*

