### **1.i Data Collection Procedures for Adverse Events**

Adverse events will be recorded in rater/interventionist log within the same day of the visit or phone call. [name] and [name] will discuss if the participants need to be withdraw when an adverse event occur within 2 days.

Should there be a serious adverse event that occurs that increases the risks to the participants, the study will be stopped, an investigation will be conducted, and a findings report will be generated before the study is resumed(see 5.d).

Data of the withdrawn subjects other than reasons of withdrawal and demographic information will be deleted and excluded from data analysis.

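### G3 plans only paired signed-rank tests to detect an intervention effect: it has no counterpart to A1's between-arm test, and G1's effect size is undefined

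*Combined protocol and SAP*

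**What the plan says.** The trial randomises 16 people 1:1 to Adapted LiFE or an attention control (A1, E1). On allocation, section 2.d says: "The REDCap module uses a blocked randomization design in which gender will be stratified to ensure balanced group sizes".

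Three places bear on the efficacy analysis:

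- **G3** states its purpose as detecting an intervention effect and names one method: "Wilcoxon signed rank tests will be used to identify trends in levels of balance, muscle strength, and habit formation". The same text is printed twice, and no other method follows.
- **A1** names different tests: "Paired t-tests will be used to test time effects, and independent t-tests will be used to test group effects of Adapted LiFE".
- **G1** says that the pilot does not test hypotheses and declines a power calculation: "Thus, sample size calculation are not necessary". It then gives the reason for the number chosen: "We select to set our sample size at 16 to evaluate feasibility and effect size for future study".

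G2 covers only descriptive statistics for demographics and feasibility outcomes. No section names the contrast, visit, scale or interval for an effect size, and none says whether A1 or G3 takes precedence.

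**The concern.** A signed-rank test is a one-sample or paired test. On the natural reading of G3 it compares visits within participants, so the control arm is never used as a comparator. It can replace A1's test of change over time, but G3 has nothing to replace A1's test between groups.

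G3 is also incomplete as a paired analysis. It does not say what is paired, or whether the arms are analysed separately or pooled. For habit there is a further choice of visits: "Habit formation will also be evaluated at T1, T2, and 1-month after post-test via phone". G3 does not say which two of the three are compared.

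Two things are at stake. First, participants repeat the same performance tests, and both arms get equal therapist contact, so some change common to both arms is plausible. A within-arm test would credit that change to Adapted LiFE. Second, a signed-rank p-value gives no between-arm effect size, which is part of G1's reason for enrolling 16.

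The reach is limited to the preliminary efficacy results and their use in planning the larger trial. The aim in C1 is "The primary aim of this study is to establish feasibility of Adapted LiFE and a RCT design", and its criteria do not depend on these tests.

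**Working it through.** **1. The plan's own figures.** 8 + 8 = 16, so A1 and G1 agree on size. There is no power or precision figure to reproduce, because G1 gives no alpha, effect or SD.

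**2. The two analysis texts side by side.**

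| Question | A1 | G3 |
|---|---|---|
| Change over time | paired t-test | signed-rank test |
| Adapted LiFE v control | two-sample t-test, not said whether on T2 values or change | nothing |
| Arms separate or pooled | not stated | not stated |
| Visits compared | not stated | not stated |
| Effect size and interval | none | none |

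The two disagree on the test over time, and only A1 has a test between groups.

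**3. What the paired test does when both arms change equally.** Assumptions, none of them from the documents: normal change scores with SD 1, the same mean shift in both arms (true between-arm difference zero), exact two-sided signed-rank test at 0.05, and a two-sample t-test on change for comparison. There were 200,000 simulated trials per scenario.

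8 v 8:

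| Shared shift (SD of change) | One arm | Exactly one of two arms | Pooled 16 | Between-arm t-test |
|---|---|---|---|---|
| 0 | 3.9% | 7.5% | 4.5% | about 5% |
| 0.3 | 9.2% | 16.8% | 18.4% | about 5% |
| 0.5 | 19.3% | 31.0% | 43.0% | about 5% |
| 0.8 | 43.1% | 49.0% | 81.9% | about 5% |

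The t-test ranged from 4.9% to 5.1%. An exact rank-sum test between arms (50,000 runs) gave the same range.

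Two hand checks:

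- At zero shift with n = 8, the rejection region is a smaller rank sum of at most 3. It holds 5 of the 2^8 = 256 sign patterns per tail, so the size is 2 × 5/256 = 3.9%.
- The chance that exactly one arm is significant is 2p(1 − p). At 0.5 SD this is 2 × 0.193 × 0.807 = 31%. At 0.8 SD it is 2 × 0.431 × 0.569 = 49%.

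With C1's 80% retention target, 0.80 × 16 = 12.8, or about 13 people, taken as 7 v 6:

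| Shared shift | Arm of 7 | Arm of 6 | Pooled 13 | Between-arm t-test |
|---|---|---|---|---|
| 0.5 | 18.7% | 11.0% | 36.2% | 5.0% |
| 0.8 | 39.9% | 24.0% | 73.0% | 5.0% |

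**4. Precision of the missing between-arm estimate**, in SD of change. Half-width of the 95% CI = t(0.975, n1 + n2 − 2) × √(1/n1 + 1/n2).

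- 8 v 8: 2.145 × √(1/8 + 1/8) = 2.145 × 0.500 = 1.07.
- 7 v 6: 2.201 × √(1/7 + 1/6) = 2.201 × 0.556 = 1.22.

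On the standardised scale at 8 v 8 (noncentral t), an observed difference of 0.5 has a 95% CI of −0.51 to 1.49. An observed 0.8 has −0.24 to 1.81.

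**5. Adjustment for the T1 value and gender.** The model has four parameters (intercept, arm, T1 value, gender), leaving 16 − 4 = 12 residual degrees of freedom, or 13 − 4 = 9. By simulation at 8 v 8 (20,000 runs), the variance of the adjusted estimate is 0.87, 0.92 and 0.98 of that of the unadjusted change-score difference at assumed T1–T2 correlations of 0.6, 0.7 and 0.8. The gain is small.

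**The case against.** The strongest reply is that the document does plan a group test, in A1, so the harm arises only if G3 is followed alone. That is correct. What is established is an unresolved conflict, not a trial with no group comparison anywhere. But an analyst would work from G3, and the choice between the two sections is open until someone makes it, possibly after seeing data. A1 also gives no estimate or interval.

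A second reply is that this is a small feasibility pilot that disclaims hypothesis testing. That limits the consequences. It does not remove them, because the plan itself sets out to detect an intervention effect and to evaluate an effect size.

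Third, the percentages rest on assumed shifts and on normal change scores. They fit the continuous measures (centre-of-pressure path, tandem walk time, dynamometry) better than the ordinal or bounded ones, such as the Berg scale or the Four-Stage test. Zero changes shrink the signed-rank sample. With two zeros in an arm of 8, six values remain, where the rate at 0.5 SD was 11%. With three zeros, five remain and the smallest two-sided p is 2/2^5 = 0.0625, so significance is impossible. No section proposes pooling either; the pooled column is there only because G3 leaves it open. Regression to the mean is at most indirect, since entry is on fall history and not on the measured scores. All of this stands, and the rates should be read as illustrations. The main point needs none of them: a paired test cannot separate an arm effect from change common to both arms.

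Finally, the repeated text in G3 might mean that a group-test sentence was lost, or it might be an accident of typesetting. Nothing here relies on it.

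**Conclusion.** The concern holds and should be fixed. G3 offers only a paired test for detecting an intervention effect, A1 plans a between-group test that G3 does not carry, no text reconciles them, and the effect size in G1 is unspecified.

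If G3 alone were used, an assumed shared improvement of 0.5 to 0.8 SD of change would give a significant result in 19% to 43% of trials within one arm of 8, and in 43% to 82% if the arms were pooled, with no true difference. A between-arm t-test would stay near 5%. The size of this depends on the assumed shift, alpha of 0.05 and normal change scores; the direction does not. The feasibility conclusions are untouched.

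**What to change.** Amend G3 and make A1 agree with it:

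- For each efficacy measure, specify an exploratory Adapted LiFE minus control difference by randomised arm at T2, with a 95% CI and a standardised effect size. Do the same at T3 for the habit index and the balance confidence scale, which the table in section 1.b schedules at T3.
- State whether the comparison uses T2 values or change from T1. Adjustment for the T1 value and gender is preferable but optional.
- For ordinal scores, a rank-sum test on change with a Hodges-Lehmann estimate is acceptable. If the Four-Stage test is reported in its two risk categories, give counts by arm.
- Label within-arm signed-rank results as descriptive, name the visits paired, and say that the arms are not pooled.
- Report numbers randomised and analysed per arm. Section 1.i says: "Data of the withdrawn subjects other than reasons of withdrawal and demographic information will be deleted and excluded from data analysis". The estimate would then cover only those not withdrawn. Section 2.g says that withdrawn participants' information is kept until study completion, so the two sections should be aligned.

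The cost is wording only, with no new data. The drawback is an imprecise estimate (half-width 1.07 SD of change at 8 v 8, 1.22 at 7 v 6), which is a weak sole basis for sizing the next trial and should be described as such.

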## **G4 Missing Outcome Data**

For feasibility outcomes, all data will be used in the final data analysis. Participants who have missing data will still be included.

